8.1.4.4 Analysis on individual components of the ACR

The primary comparison (BKZ vs. placebo) will also be repeated for all individual components of the ACR50 response to explore the effect of the signs and symptoms of the individual components on the composite endpoint. Since all ACR components are continuous variables (eg, change from Baseline in TJC), an analysis of covariance (ANCOVA) with treatment, region, and Prior TNF α inhibitor exposure as fixed effects and the Baseline value as covariate will be used for the analysis. Missing data imputation described in [Section 4.2.2](#) will be successively applied for each component.

The following 4 attributes describe the hypothetical estimand that will be used to define the treatment effect of interest for each of the 7 ACR components:

- Population = Subjects enrolled according to the protocol-specified inclusion/exclusion criteria and randomized to IMP
- Subject level outcome = Change from Baseline in the ACR components at Week 16

- Intercurrent event handling = An intercurrent event is defined as discontinuation of study treatment prior to Week 16. This estimand targets the treatment difference in a scenario where withdrawal from study treatment does not occur, such that outcomes for subjects without an intercurrent event are as observed, and outcomes for subjects with an intercurrent event are treated successively according to the 2 following hypothetical strategies:
 - (a) as they had completed treatment through Week 16. In that strategy, missing data or non missing data after IE (reset as missing) will be imputed using MI as though they had completed the randomized study treatment through Week 16.
 - (b) as they had completed the randomized study treatment through Week 16 but on placebo. In that strategy, missing data or non missing data after IE (reset as missing) will be imputed using Reference-Based MI, in which the MI model is based on data from the Placebo group.
- Population-level summary measure = The difference in the adjusted means between BKZ and placebo.

For the results obtained using the 2 MI methods, the SAS® PROC MIXED will be used to run the ANCOVA model. The inferential statistics obtained from each model will be displayed in a single table.

For all variables, the following statistics will be presented:

- the adjusted least-square means (LSM) and standard error (SE) by treatment group,
- for the comparison between placebo and BKZ; the difference between the LSM, the associated 95% CI for the contrasts, and the corresponding p-value.

An additional table will present the descriptive statistics for the 2 treatment groups for each ACR component variable at Week 16. Those statistics will be the mean and SE, median, minimum, and maximum after MI.

8.1.4.5 Analyses using treatment policy strategy imputation for missing data

The treatment policy strategy for addressing the intercurrent events will be considered. In this analysis, all available data at Week 16 will be considered regardless of the occurrence of intercurrent events. This analysis will use the same models specified for the primary analyses where subjects are analyzed according to their randomized treatment, even if they discontinued study treatment for any reason prior to Week 16 and were no longer on the randomized study treatment when the assessment was performed at Week 16.

In the context of this analysis, in addition to the statistics provided in the context of MI, the number of observed ACR50 responses regardless of the existence of IE will be also reported.

The following 4 attributes describe the treatment policy strategy analysis is detailed below:

- Population = Subjects enrolled according to the protocol-specified inclusion/exclusion criteria and randomized to IMP
- Subject-level outcome = ACR50 at Week 16
- Intercurrent event handling = Discontinuation of study medication for any reason will be handled by using the data as observed irrespective of the intercurrent event occurring.

- Population-level summary measure = Conditional odds ratio comparing ‘BKZ and other medication as needed’ to ‘placebo and other medication as needed’.

8.1.4.6 Analysis on Observed cases

An observed case (OC) analysis will additionally be conducted, where only observed data for subjects who are still on the randomized treatment at Week 16 are included. Subjects with missing data at Week 16 or who have prematurely discontinued study treatment at or prior to Week 16 will be treated as missing and missing data will not be replaced.

The following 4 attributes describe the estimand that will be used to define the treatment effect of interest for the OC analysis:

- Population = Subjects enrolled according to the protocol-specified inclusion/exclusion criteria and randomized to IMP
- Subject-level outcome = ACR50 at Week 16 while on randomized treatment
- Intercurrent event handling = A “while on randomized treatment” strategy will be implemented.
- Population-level summary measure = Conditional OR comparing BKZ to placebo.

The same analysis model as used for the primary efficacy analysis will be conducted on the RS.

8.1.4.7 Tipping point analysis

The degree of the departure from the MAR assumption to overturn conclusions from the primary analysis will be investigated in a tipping point analysis. This analysis will be performed on the monotone missing data and only if the primary analysis is significant at $\alpha=0.05$. Intermittent missing data will be imputed using the MCMC method. In this analysis, it will be assumed that subjects who have missing data and are randomized to BKZ have a lower probability of response compared to subjects who have missing data and are randomized to placebo.

The analysis will be primarily conducted on the binary response endpoint itself in considering the worst-case scenario that subjects who have missing ACR50 response will be set as non-responders if they are randomized to BKZ, and as responders if they are randomized to Placebo. If the result tips, then the tipping point analysis will be reconducted on the ACR50 endpoint after having delta-adjusted each individual component of the ACR50 endpoint. For both analyses, the same model as used for the primary efficacy analysis will be conducted on the RS. If the delta parameter value for which the study conclusion under MAR is reversed is plausible, the conclusion under MAR will then be questionable.

Refer to [Section 4.2.2.4](#) for more details on the methodology.

8.1.4.8 Analyses including COVID-19 impact

To assess the impact of the COVID-19 pandemic on the primary efficacy endpoint, 2 sensitivity analyses will be conducted using the same analysis method as the primary analysis ([Section 8.1.2](#)):

- on the COVID-19-free Set

- by COVID-19 period (pre- during -post as determined by the Week 16 date).

8.2 Statistical analysis of the secondary efficacy variables

8.2.1 Derivation of secondary efficacy variables

The primary and supportive analysis methods of secondary efficacy variables for which the derivation method is provided below are described in [Section 8.2.2](#) and [Section 8.2.3](#).

For the other secondary variables which are not part of the testing hierarchy, there is no priority designated between methods described as primary and supportive analysis methods.

8.2.1.1 HAQ-DI: Change from Baseline at Week 16

The derivation for HAQ-DI is described in [Section 8.1.1.3](#) (The analysis of this variable is already covered in [Section 8.1.4.4](#)).

Change from Baseline at Week 16 in HAQ-DI is the 2nd endpoint in the sequential testing hierarchy ([Table 7-4](#)).

8.2.1.2 Psoriasis Area and Severity Index 90 (PASI90) at Week 16 (in subjects with PSO involving at least 3% of BSA at Baseline)

PASI scoring of psoriatic plaques is based on 3 criteria:

- redness (R),
- thickness (T),
- scaliness (S).

Severity is rated for each index (R, S, T) on a 0-4 scale (0 = none, 1 = slight, 2 = moderate, 3 = marked, and 4 = very marked).

The body is divided into 4 areas comprising:

- head (h),
- upper extremities (u),
- trunk (t),
- lower extremities (l).

In each of these areas, the fraction of total surface area affected is graded on a 0-6 scale (where 0 = 0% [clear], 1 = >0% to <10%, 2 = 10% to <30%, 3 = 30% to <50%, 4 = 50% to <70%, 5 = 70% to <90%, and 6 = 90% to 100%).

The various body regions are weighted to reflect their respective proportion of BSA. The composite PASI score is then calculated by multiplying the sum of the individual-severity scores for each area by the weighted area-of-involvement score for that respective area, and then summing the 4 resulting quantities as follows:

$$\begin{aligned} \text{PASI} &= (0.1 \times (R_h + T_h + S_h) \times A_h) \\ &\quad + (0.2 \times (R_u + T_u + S_u) \times A_u) \\ &\quad + (0.3 \times (R_t + T_t + S_t) \times A_t) \end{aligned}$$

$$+(0.4 \times (R_l + T_l + S_l) \times A_l)$$

where

R_h, R_u, R_t, R_l = redness score of plaques on the head, upper extremities, trunk, and lower extremities, scored 0-4 respectively;

T_h, T_u, T_t, T_l = thickness score of plaques on the head, upper extremities, trunk, and lower extremities, scored 0-4 respectively;

S_h, S_u, S_t, S_l = scaliness score of plaques on the head, upper extremities, trunk, and lower extremities, scored 0-4 respectively;

A_h, A_u, A_t, A_l = numerical value translation of % area of psoriatic involvement score for the head, upper extremities, trunk, and lower extremities, scored from 0-6 respectively.

The highest potential PASI score is 72 for severe disease; the lowest is 0 for no psoriasis lesions. PASI scores are treated as continuous. If a subject is missing 1 or 2 severity measurements for a certain region, the average of the remaining non-missing severity measurement(s) within that region will be utilized to substitute for the missing severity measurement(s) in that region. If the area of affected skin and/or all severity measurements for up to 2 regions are missing, then the missing $(R+T+S) \times A$ for a region will be substituted by the average of the available $(R+T+S) \times A$. Otherwise, the PASI score will be set to missing.

The percent improvement in PASI scores from Baseline will be then computed as:

$$\text{Percent improvement from Baseline} = 100 \times \frac{\text{Baseline PASI} - \text{Post Baseline PASI}}{\text{Baseline PASI}}$$

If a subject has experienced an improvement, this measure will be positive. If a subject has experienced a worsening in their condition, this measure will be negative.

PASI90 is a binary variable equal to 1 if the percentage improvement from Baseline in the PASI scores is 90% or greater and 0 if the percentage improvement from Baseline is less than 90%.

PASI90 is the 3rd endpoint in the sequential testing hierarchy ([Table 7-4](#)).

8.2.1.3 SF-36 PCS: Change from Baseline at Week 16

The SF-36 (Version 2, standard recall) is a 36-items generic health-related quality of life instrument that uses a recall period of 4 weeks. Items are grouped into 8 domains as follows:

- Physical Functioning (10 items)
- Role Physical (4 items)
- Bodily Pain (2 items)
- General Health (5 items)
- Vitality (4 items)
- Social Functioning (2 items)
- Role Emotional (3 items)
- Mental Health (5 items)

The concepts represented by these domains contribute to physical, mental, and social aspects of health-related quality of life.

In addition to domain scores, the PCS and MCS scores are calculated from the 8 domains (excluding the Health Transition item). Component scores reflect the impact of each domain on physical and mental health status.

The norm-based T-scores for the 2 SF-36 component summary (PCS and MCS) and the 8 domains are standardized with a mean of 50 and a standard deviation (SD) of 10 in the general US population (Maruish, 2011). An individual respondent's score that falls outside the T-score range of 45 to 55 should be considered outside the average range for the US general population. When considering group-level data, a score below 47 should be considered indicative of impaired functioning within that health domain or dimension. Similar to individual respondent data, group mean scores of 47 or greater should be considered average or above average as compared to the general US population. Higher scores indicate a better health status.

For the calculation of the SF-36 norm-based T-scores for the 8 domains and the PCS and MCS, the scoring software Optum's PRO CoRE (version 1.4) will be used. The software uses updated 2009 U.S. population norms and applies a Full Missing Score Estimation method as follows:

- A health domain score (except the Physical Functioning domain) will be estimated provided that at least one non-missing response is available within that domain.
- For the Physical Functioning domain, item response theory will be used to develop a model for estimates of the missing score.
- Regression methods will then be applied to estimate the PCS and MCS on the basis of the available domains.

Change from Baseline at Week 16 in SF-36 PCS score is the 4th endpoint in the sequential testing hierarchy (Table 7-4).

8.2.1.4 MDA at Week 16

MDA is a state of disease activity deemed a useful target of treatment by both the subject and physician, given current treatment possibilities and limitations. The criteria that need to be met are based on key outcome measures in PsA and are shown below:

- Tender Joint Count ≤ 1
- Swollen Joint Count ≤ 1
- PASI ≤ 1 (for subjects with PSO involving at least 3% of BSA at Baseline) or BSA $\leq 3\%$
- PtAAP (VAS) ≤ 15 mm
- PGA-PsA (VAS) ≤ 20 mm
- HAQ-DI ≤ 0.5
- Tender enthesial points ≤ 1 (LEI ≤ 1)

A subject has achieved MDA if 5 or more of the 7 above criteria are fulfilled.

The enthesitis instrument of the study (ie., LEI) will be used to determine whether a subject has ≤ 1 tender enthesial point.

The following rule will be applied for subjects with BSA < 3 at Baseline: Subjects with BSA < 3 at Baseline will always meet the criteria PASI ≤ 1 or BSA ≤ 3 except in the cases where a post-Baseline BSA score > 3 is observed.

MDA at Week 16 is the 5th endpoint in the sequential testing hierarchy (Table 7-4).

8.2.1.5 ACR20 and ACR70 response at Week 16

The ACR20 and ACR70 responses are defined based on respectively 20% and 70% or greater improvement from Baseline in the same measures than the primary endpoint. See Section 8.1.1 for details.

8.2.1.6 Proportion of subjects with an Investigator’s Global Assessment (IGA) score of 0 (clear) or 1 (almost clear) AND at least a 2-grade reduction from Baseline at Week 4 and Week 16 in the subset of subjects with psoriatic skin lesions at Baseline

A static IGA for psoriasis will be used to assess disease severity in all subjects during the study. Investigator will assess the overall severity of PSO using the following 5-point scale specified in Table 8-3 .

Table 8-3: Five-point IGA

Score	Short description	Definition
0	Clear	No signs of PSO; post-inflammatory hyperpigmentation may be present
1	Almost clear	No thickening; normal to pink coloration; no to minimal focal scaling
2	Mild	Just detectable to mild thickening; pink to light red coloration; predominately fine scaling
3	Moderate	Clearly distinguishable to moderate thickening; dull to bright red, moderate scaling
4	Severe	Severe thickening with hard edges; bright to deep dark red coloration; severe/coarse scaling covering almost all or all lesions

IGA=Investigator’s Global Assessment; PSO=psoriasis

The IGA response is defined as clear [0] or almost clear [1] assessment with at least a two-grade category improvement from Baseline, meaning that this parameter will be only evaluable for subjects with psoriatic skin lesions (IGA score ≥ 2) at Baseline.

Note that per protocol and device setting, only subjects with BSA $\geq 3\%$ at Baseline will have IGA assessed at post-Baseline visits.

For some subjects with BSA $\geq 3\%$ at Baseline, IGA data have not been captured at Week 4 and Week 16 visits when BSA $< 3\%$ at those visits. To address that, additional supportive analyses will be performed in which these subjects will be considered as IGA responders at the respective visit.

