4.2.2.1 Non-responder imputation

For binary endpoints, the non-responder imputation (NRI) analysis, also described above as the primary composite estimand, will consider the following subjects as “non-responders” for the timepoint of interest:

- Subjects with missing data at the timepoint of interest. In the case of ACR50, nonresponse is imputed if ACR50 cannot be derived (ie, derived as “missing”) based on available ACR components. (Section 8.1.1).

- Subjects remaining in the study at the timepoint of interest but discontinuing study treatment before the timepoint of interest (data after IE).
- Subjects with missing Baseline value (for composite or non-composite binary variables based on change(s) from Baseline of continuous endpoint(s)).

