Subjects with psoriatic nail disease will have a target nail selected at the Baseline Visit for evaluation using the mNAPSI. The nail selected should be the most affected nail observed at Baseline and should be the only one assessed throughout the study. The target nail will be scored (from 0 to 3) for onycholysis/oil drop dyschromia, nail plate crumbling, and pitting and will be

scored (0 for “no” or 1 for “yes”) for leukonychia, nail bed hyperkeratosis, splinter hemorrhages, and red spots in the lunula. The total score (also called the mNAPSI score) will then range from 0 to 13 with higher scores indicative of more severe nail disease.

If any of the 7 response items that contribute to mNAPSI is present, while other items are missing (ie, partial mNAPSI data), then the missing items are assumed to be 0 for the mNAPSI calculation. In some cases, the data may be captured in such a way that only non-zero component scores are present in the database. Again, those components that are not present are simply assumed to be 0 for the mNAPSI calculation

Analyses will be restricted to the subset of subjects with psoriatic nail disease at Baseline (defined as mNAPSI score>0).

Change from Baseline in mNAPSI and mNAPSI resolution (mNAPSI=0 at post-Baseline assessments) will be analyzed for subjects with psoriatic nail disease at Baseline (mNAPSI score>0) at Week 4, 8, 12, and 16.

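### The PASI missing-region rule makes no exception for a region recorded as clear (area grade 0), so a contribution known to be 0 can be replaced and PASI90 (H3) can be misclassified if severity is left blank in clear regions

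*SAP*

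**What the plan says.** SAP section 8.2.1.2 builds PASI from four regions. Severity (redness, thickness, scaliness) is graded 0–4, where 0 is none. Area is graded 0–6, and the scale begins "0 = 0% [clear], 1 = >0% to <10"%. On the weights it says "The various body regions are weighted to reflect their respective proportion of BSA": 0.1 for the head, 0.2 for the upper extremities, 0.3 for the trunk and 0.4 for the lower extremities.

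The missing-data rule for whole regions begins "If the area of affected skin and/or all severity measurements for up to 2 regions are missing". The missing product for such a region is then replaced by the average of the available products. For anything beyond that, "Otherwise, the PASI score will be set to missing". The response is defined by "PASI90 is a binary variable equal to 1 if the percentage improvement from Baseline in the PASI scores is 90% or greater".

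PASI90 at Week 16 is H3 in the fixed sequence (section 4.5). Under section 4.2.2.1 non-responders include "Subjects with missing data at the timepoint of interest".

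**The concern.** The trigger is worded as area and/or all severities missing. It therefore covers a region whose area was recorded as 0 and whose severities are blank. For that region the product is not unknown: any severity multiplied by area 0 is 0. Read literally, the rule discards this known 0 and inserts the average of the other regions, which may still carry disease. If three or four regions are in this state, PASI becomes missing and NRI scores the subject as a failure, even with fully clear skin.

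The SAP does not say whether severity is recorded as 0 or left blank when a region is clear. It does report conditional capture for related measures. For IGA in some subjects with Baseline BSA of at least 3%, "IGA data have not been captured at Week 4 and Week 16 visits" when BSA had fallen below 3% (section 8.2.1.6). For mNAPSI, "In some cases, the data may be captured in such a way that only non-zero component scores are present in the database", and absent items are then taken as 0 (section 8.3.1.17). No equivalent statement is made for PASI.

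At stake is a formally tested endpoint that must succeed before H4 and H5 can be tested. PASI75, PASI100, the ACR50/PASI90 and ACR50/PASI100 composites and the PASI≤1 criterion of MDA (H5) use the same score.

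**Working it through.** **The plan's own figure.** Section 2.4.2 gives 99% power for PASI90 at 38% versus 10%, with half of 390 subjects evaluable, that is 130 versus 65.

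- Pooled rate = (65×0.10 + 130×0.38)/195 = 0.2867.
- SE under the null = √[0.2867×0.7133×(1/65+1/130)] = 0.0687.
- SE under the alternative = √[0.10×0.90/65 + 0.38×0.62/130] = 0.0565.
- Continuity correction = 0.5×(1/65+1/130) = 0.0115.
- z = (0.28 − 0.0115 − 1.96×0.0687)/0.0565 ≈ 2.37, so power is 99.1%. The odds ratio is (0.38/0.62)/(0.10/0.90) = 5.52. Both agree with the SAP.

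This calculation does not involve the PASI derivation rule.

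**The rule on illustrative subjects.** Write P for a region's (R+T+S)×A. Then PASI = 0.1·P(head) + 0.2·P(upper) + 0.3·P(trunk) + 0.4·P(lower). The cases are constructed. Blank means area grade 0 with no severity recorded.

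1. *Week 16, two regions blank.* Baseline PASI 18; head and trunk blank; upper and lower P = 3 each.
   - By the formula: 0.2×3 + 0.4×3 = 1.8, improvement (18−1.8)/18 = 90.0%, responder.
   - Literal rule: head and trunk become 3, PASI 3.0, improvement (18−3)/18 = 83.3%, non-responder.
2. *Week 16, away from the exact threshold.* Baseline 17.4; head and upper blank; trunk and lower P = 2 each.
   - By the formula: 0.7×2 = 1.4, 92.0%, responder.
   - Literal rule: PASI 2.0, 88.5%, non-responder.
3. *Week 16, PASI≤1 crossed as well.* Baseline 10.2; head and trunk blank; upper graded 0; lower P = 2.
   - By the formula: 0.4×2 = 0.8, 92.2%, responder.
   - Literal rule: head and trunk become (0+2)/2 = 1, PASI 0.1 + 0.3 + 0.8 = 1.2, 88.2%, non-responder. PASI≤1 is met by the formula and missed by the rule.
4. *A case that does not flip.* As case 3, but only the trunk is blank. The trunk becomes (0+0+2)/3 = 0.667, PASI 0.2 + 0.8 = 1.0, 90.2%, still a responder.
5. *Three or four regions blank.* With Baseline 10.2, three clear regions and lower P = 2, the formula gives 0.8 (92.2%). With four clear regions it gives 0 (100%). Under the literal rule PASI is missing in both, hence NRI non-response.
6. *Baseline, two regions blank.* Head and upper blank; trunk P = 12, lower P = 6. At Week 16 only lower P = 2 remains (PASI 0.8), with the clear regions graded 0.
   - By the formula: Baseline 0.3×12 + 0.4×6 = 6.0, improvement 86.7%, non-responder.
   - Literal rule: head and upper become (12+6)/2 = 9, Baseline 6.0 + 0.3×9 = 8.7, improvement (8.7−0.8)/8.7 = 90.8%, responder.

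Cases 3, 4 and 6 need mixed capture, with some clear regions graded 0 and others left blank. If case 6 left clear regions blank at Week 16 too, three would be blank and PASI would be missing. Cases 1, 2 and 5 need only that clear regions are consistently blank.

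**The case against.** The premise is not in the SAP. Severity has its own 0 grade, so a clear region can be fully recorded. Whether it is depends on the CRF or device, which is not shown. The sentence also says that what is replaced is the missing regional product; with area 0 recorded, that product can fairly be regarded as not missing. The section adds that PASI is 0 when there are no lesions, which the literal reading would contradict for a clear subject with blank severities. The IGA gap is non-capture of a whole instrument, and for mNAPSI the authors knew of the issue and wrote a rule, so neither shows that PASI has the problem. All of this stands. It makes the point an ambiguity with a possible consequence, not a demonstrated error. It does not remove the ambiguity, because the trigger wording supports the other reading equally well and two programmers could derive different PASI90 values.

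Some further protection exists. PASI90 also has observed-case and modified-composite MI analyses, so a PASI set to missing is not a failure in every analysis. These do not undo a substituted score. For MDA, the skin criterion can also be met through BSA.

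A reader might also infer that filling up to two unexamined regions from the others is wrong, because the estimand counts missing data as non-response. The SAP does not support that. Substituting up to two of four regions is a pre-specified proration of the kind used for joint counts, LEI and SPARCC. NRI applies only once the endpoint cannot be derived. An exception for the PASI responses alone would make them inconsistent with the PASI score used in MDA.

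**Conclusion.** The point holds as a gap in the derivation of a hierarchy endpoint. The rule as worded reaches regions whose contribution is already known to be 0, and nothing in the section excludes them. If clear regions are left ungraded, a subject can be moved across the 90% threshold in either direction. At Week 16 responders can be lost (90.0% to 83.3%; 92.0% to 88.5%; missing and hence failure with three or four such regions). Through Baseline a responder can be gained (86.7% to 90.8%).

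This rests on two assumptions: that severity is blank in at least some clear regions, and, where one or two regions are affected, that the subject is near the threshold. The document gives no frequency for either.

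A reader might infer that PASI90 is in fact misclassified, that the bias runs against bimekizumab, or that the 99% power is overstated. None of these is supported. The blank-severity premise is unstated, the direction can reverse at Baseline, the power figure reproduces, and there is no basis for assuming any particular loss of responders.

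**What to change.** Add to section 8.2.1.2: when a region's area grade is 0, (R+T+S)×A for that region is 0 whether or not severity was recorded, at Baseline and at every post-Baseline visit. Then limit the substitution, and the count of up to two regions, to regions whose area is missing, or whose area is 1–6 with all severities missing. Leave the fill-in of unexamined regions as it is.

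The cost is two sentences and one programming condition. If severity is always recorded as 0 in clear regions, the change alters no result, so there is no scientific downside.

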2.2.2 Secondary variables

2.2.2.1 Secondary efficacy variables

The secondary efficacy variables are as follows:

- Change from Baseline in Health Assessment Questionnaire - Disability Index (HAQ-DI) at Week 16
- Reduction of 90% from Baseline in Psoriasis Area and Severity Index (PASI90 response) at Week 4 and Week 16 in the subgroup of subjects with PSO involving at least 3% body surface area (BSA) at Baseline
- Change from Baseline in the Short-Form 36-item Health Survey (SF-36) Physical Component Summary (PCS) score at Week 16
- Minimal Disease Activity (MDA) response at Week 16
- ACR20 response at Week 16
- ACR70 response at Week 16
- Proportion of subjects with an Investigator Global Assessment (IGA) score of 0 (clear) or 1 (almost clear) AND at least a 2-grade reduction from Baseline at Week 4 and Week 16 in the subset of subjects with psoriatic skin lesions at Baseline
- Change from Baseline in the Patient's Assessment of Arthritis Pain (PtAAP) at Week 16
- Change from Baseline in Psoriatic Arthritis Impact of Disease-12 (PsAID-12) total score at Week 16

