8.2.2 Primary analysis of secondary efficacy variables

The secondary efficacy variables will be analyzed for all subjects in the RS.

As indicated in [Table 7-4](#), there are 4 secondary endpoints included in the testing hierarchy that will be tested in a chronological order until one is failed to be statistically significant.

For the other secondary endpoints (which are not part of the testing hierarchy), the p-values produced by the statistical models will be considered nominal since these endpoints are not controlled for multiplicity.

For the secondary composite and non-composite binary endpoints, the same estimand structure (composite estimand) as the one defined for the primary efficacy analysis of the primary efficacy endpoint ([Section 8.1.2](#)) will be used. The NRI approach for handling missing data and the same analysis model will be considered, and the analysis results will be presented similarly.

The statistical hypothesis for the binary variables at Week 16 is that the conditional odds ratio in the BKZ group compared with placebo treatment group is equal to 1. For the secondary continuous endpoints, the analysis will evaluate the hypothetical estimand as defined below:

- Population = Subjects enrolled according to the protocol-specified inclusion/exclusion criteria and randomized to IMP.
- Subject level outcome = variable as stated in [Section 2.2.2](#)
- Intercurrent event handling = An intercurrent event is defined as discontinuation of study treatment prior to Week 16. A hypothetical strategy for addressing intercurrent events will be implemented. This estimand targets the treatment difference in a scenario where withdrawal from study treatment does not occur, such that outcomes for subjects without an IE are as observed, and outcomes for subjects with an IE are treated as though they had completed treatment through Week 16 but on placebo. A MI strategy will be used to impute any missing data and observed data after IE which will be set to missing prior to running MI. Such data will be imputed using Reference-Based MI, in which the MI model is based on data from the placebo group.
- Population-level summary measure = the difference in the adjusted means between BKZ 160mg Q4W and placebo.

The same analysis model and imputation strategy for handling missing data as in [Section 8.1.4.4](#) will also be considered. The analysis results will be presented similarly as for this analysis on the individual ACR components.

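### The IGA response subset has no BSA limit although post-Baseline IGA is collected only at Baseline BSA ≥3%, so the NRI rates are diluted in both arms by an unknown amount

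*SAP*

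**What the plan says.** The endpoint is IGA 0 or 1 with at least a 2-grade reduction, at Weeks 4 and 16. Section 2.2.2.1 places it "in the subset of subjects with psoriatic skin lesions at Baseline". The PASI90 item in the same list is limited to BSA ≥3%; the IGA item is not. Section 8.2.1.6 makes the subset concrete: "meaning that this parameter will be only evaluable for subjects with psoriatic skin lesions (IGA score" ≥2) at Baseline.

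Section 8.2.1.6 describes IGA collection in three ways:

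- "A static IGA for psoriasis will be used to assess disease severity in all subjects during the study".
- "Note that per protocol and device setting, only subjects with BSA" ≥3% at Baseline have IGA at post-Baseline visits.
- For some subjects with Baseline BSA ≥3%, "IGA data have not been captured at Week 4 and Week 16 visits when BSA" is <3% at those visits. For them, "additional supportive analyses will be performed in which these subjects will be considered as IGA responders at the respective visit".

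For secondary binary endpoints, Section 8.2.2 says: "The NRI approach for handling missing data and the same analysis model will be considered". Section 4.2.2.1 lists among the non-responders: "Subjects with missing data at the timepoint of interest". It makes no exception for data that were never due to be collected.

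**The concern.** Two groups have no IGA for reasons unrelated to dropout.

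- **Group A:** IGA ≥2 and BSA <3% at Baseline. They meet the written subset definition, but their IGA is not assessed after Baseline.
- **Group B:** Baseline BSA ≥3%, BSA <3% at the visit, IGA not captured. Their data are missing because the skin improved.

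Under NRI both groups count as failures. Group A dilutes both arms alike. Group B removes responders, and takes more percentage points from the arm with more of them. At stake are the reported rates, and their difference, for a listed secondary endpoint at two timepoints. The denominator is also unclear: two programmers could read Section 8.2.1.6 differently and report different rates.

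**Working it through.** **How each planned method treats the two groups**

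| Method (SAP section) | Group A | Group B |
|---|---|---|
| NRI (4.2.2.1, 8.2.2) | failure | failure |
| Supportive analysis (8.2.1.6, 8.3.1.9) | not covered | all responders |
| Observed cases (4.2.1.3, 4.2.1.6, 8.2.3) | dropped | dropped |
| Modified composite with multiple imputation (MI) (4.2.2.2.1, 8.1.4.3) | imputed from subjects with larger BSA | imputed without using BSA |

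The MI row follows from the imputation model, which contains the randomization strata and the variable's own visits but no BSA term. Section 8.2.3 restricts the imputation to Baseline BSA ≥3% for PASI90; it has no matching line for IGA.

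**Inputs.** The SAP gives no IGA rate, power or sample size, so there is no IGA figure to reproduce. Section 2.4.2 gives the PASI90 planning values used here as stand-ins: 38% vs 10%, with 50% of the planned sample at BSA ≥3%. From 260 and 130 subjects that leaves 130 and 65.

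**Check of the borrowed inputs.** The stated PASI90 power is 99%. Without continuity correction:

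- Pooled rate = (0.10 + 2 × 0.38)/3 = 0.2867.
- Null SE = √[0.2867 × 0.7133 × (1/65 + 1/130)] = 0.0687.
- Alternative SE = √[0.10 × 0.90/65 + 0.38 × 0.62/130] = 0.0565.
- z = (0.28 − 1.96 × 0.0687)/0.0565 ≈ 2.57, so power is 99.5%.

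With continuity correction the power is 99.1%. Both agree with the plan.

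**Effect on the NRI rate.** Let p be the true response among subjects with Baseline BSA ≥3%, s the number of Group A subjects per subject with Baseline BSA ≥3%, and q the share of true responders whose IGA was not captured. Then

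NRI rate = p(1 − q)/(1 + s).

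The SAP gives neither s nor q, so the values below are assumptions.

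| s | q | Active | Placebo | Difference (points) |
|---|---|---|---|---|
| 0 | 0 | 38.0% | 10.0% | 28.0 |
| 0.1 | 0 | 34.5% | 9.1% | 25.5 |
| 0.25 | 0 | 30.4% | 8.0% | 22.4 |
| 0.5 | 0 | 25.3% | 6.7% | 18.7 |
| 1 | 0 | 19.0% | 5.0% | 14.0 |
| 0 | 0.1 | 34.2% | 9.0% | 25.2 |
| 0 | 0.25 | 28.5% | 7.5% | 21.0 |
| 0.5 | 0.25 | 19.0% | 5.0% | 14.0 |

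In the row s = 0, q = 0.25, the same q costs the active arm 9.5 points and placebo 2.5.

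**The all-responder rule.** Table 8-3 grades thickening, colour and scaling, not affected area. BSA <3% therefore does not establish IGA 0/1 or a 2-grade drop. If a share u of true non-responders also has BSA <3% and no IGA, the rule gives p + (1 − p)u. With u = 0.1 (assumed):

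- Active: 0.38 + 0.62 × 0.1 = 44.2%.
- Placebo: 0.10 + 0.90 × 0.1 = 19.0%.
- Difference: 25.2 points.

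**What the two results bound.** With q = 0.25 and u = 0.1, each arm's true rate lies between its two results: 28.5% to 44.2% for active and 7.5% to 19.0% for placebo. The true difference of 28 points does not lie between the two reported differences, 21.0 and 25.2. The pair bounds each arm's rate, not the treatment difference.

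**The case against.** The strongest reply is that little depends on this. IGA response is outside the hierarchy in Section 4.5, its p-values are nominal (Section 8.2.2), and Section 8.2.1 gives no method priority for such endpoints. Group A is fixed by a Baseline characteristic, so randomization balances it and the dilution cannot create a treatment effect. Observed cases removes Group A. For Group B the SAP discloses the gap, plans the all-responder analysis, and in Section 8.3.1.9 adds by-visit summaries of observed BSA. The BSA note directly follows the sentence on evaluability and may be meant to limit the subset.

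Most of this stands, and it rules out stronger readings that a reader might infer:

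- **That the improvers' IGA is uncollected by design.** The SAP states the by-design limit only for Baseline BSA <3%. For improvers it reports non-capture in some subjects at some visits.
- **That no planned analysis takes Group A out.** Observed cases does, although it loses Group B as well.
- **That the 50% assumption in Section 2.4.2 gives the dilution.** It is a share of all subjects, not of those with IGA ≥2. Subjects with Baseline IGA 0 or 1 are outside the subset and probably concentrated below 3% BSA. The row s = 1 needs as many subjects with IGA ≥2 below 3% BSA as there are measured subjects, so it is an extreme.
- **That the reported rates are simply wrong, or that the trial's conclusions are at risk.** The direction under NRI is known; the size is not, and nothing confirmatory depends on it.

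What the reply does not remove is the unstated denominator. The SAP never says that the BSA note limits the subset, and none of the planned methods handles both groups properly.

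**Conclusion.** The point holds in limited form. As written, NRI makes subjects with IGA ≥2 and BSA <3% at Baseline structural non-responders in both arms, which pulls down the rates and their difference. Uncaptured improvers lower the NRI rates further. The supportive analysis for them is the opposite extreme rather than a correction, and observed cases and MI do not resolve it.

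The size cannot be derived from the SAP. With the PASI90 rates as stand-ins, s = 0.25 turns 38% vs 10% into 30.4% vs 8.0%, a loss of 5.6 points in the difference (28.0 − 22.4). This rests on an assumed s and on PASI90 rates standing in for IGA. The matter is a descriptive secondary result and an ambiguous denominator; confirmatory conclusions are unaffected.

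**What to change.** 1. In Sections 2.2.2.1, 8.2.1.6 and 8.3.1.9, define the IGA analysis subset for NRI and MI as Baseline IGA ≥2 and Baseline BSA ≥3%, matching PASI90. Add the corresponding IGA line to Section 8.2.3.
2. Reconcile the statement that all subjects are assessed with the note limiting post-Baseline IGA to Baseline BSA ≥3%.
3. Where IGA is uncaptured at BSA <3%, present the NRI and all-responder results together, labelled as lower and upper bounds on each arm's response rate. State that they do not bound the treatment difference.

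The cost is SAP text, a denominator flag and table labels; both analyses in step 3 are already planned. The downside is a smaller subset and a narrower population for a listed secondary variable. The endpoint label must therefore say BSA ≥3%, and the change belongs in Section 3.10 if the protocol defines the subset by skin lesions alone.
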